## List of Abbreviations

COI	Conflict of Interest
DSMP	Data and Safety Monitoring Plan
GDM	Gestational Diabetes
HIPAA	Health Insurance Portability and Accountability Act
ICF	Informed Consent Form
IRB	Institutional Review Board
OPRS	Office for the Protection of Research Subjects
PHI	Protected Health Information
PI	Principal Investigator
SMC	Safety monitoring committee

## 1.0 Project Summary/Abstract

Women with a history of gestational diabetes (GDM) are at high risk of developing diabetes in the future. Lifestyle intervention with diet and exercise have been shown to help reduce this risk. Sleep disturbances are emerging as risk factors for incident diabetes. Studies have shown that those sleeping <5-6 hours/day had 5-45% increase in the risk of diabetes. We have also shown that in women with a prior history of GDM, those reporting sleeping <6 hours/night had a significantly higher fasting glucose levels. In healthy volunteer who were short sleepers, sleep extension in a few studies have been shown to improve glucose metabolism. Therefore, in this study, we propose to test the effects of 6-week sleep extension, using technology-assisted sleep intervention, in women with a history of GDM and short sleep on glucose metabolism by randomized controlled study.

## 2.0 BACKGROUND/SCIENTIFIC RATIONALE

Gestational diabetes mellitus (GDM) affects 4-9% of pregnant women . Women with a history of GDM are at a 7-fold higher risk of developing future type 2 diabetes compared to those with normoglycemia during pregnancy . Public health impact of GDM is significant as it was estimated that 10-31% of parous women with type 2 diabetes had a prior history of GDM. While risks of future diabetes include traditional factors such as obesity, physical inactivity and family history of diabetes, sleep is increasingly recognized as an independent risk factor . Despite the findings that insufficient sleep in women with a prior history of GDM is common, and associated with impaired glucose metabolism, our present understanding of the effects of sleep extension on glucose metabolism and future diabetes risk in these women is very limited.

Insufficient sleep has been shown to increase diabetes risk by multiple pathways. Experimental sleep restriction resulted in increased insulin resistance without adequate compensatory increase in insulin secretion. This is likely a result of changes in appetite regulating hormones promoting hunger and weight gain, alterations in inflammatory markers, changes in energy expenditure and abnormal adipocyte function .

The primary aim of this study is to evaluate the effects of a sleep extension intervention in women with a prior history of GDM and habitual short sleep duration on the outcomes of glucose metabolism. **This proposal is based on recent observations and newly developed sleep intervention from our group.** (1) Women with a prior history of GDM who reported sleeping ≤6h/night had significantly higher fasting glucose and glucose response following oral glucose tolerance test than those sleeping >6h/night . (2) Half of the women with a prior history of GDM reported insufficient sleep ≤6h/night  (3) A pilot study of a 2-week behavioral sleep optimization in adults without

diabetes who had habitual short sleep duration led to improved fasting insulin resistance. (4) A pilot trial of our newly developed technology-assisted behavioral sleep optimization intervention in individuals with short sleep duration demonstrated a clinically significant sleep duration increase (median 35 minutes). **Therefore, this proposal seeks to improve glucose metabolism in women with a prior history of GDM and habitual short sleep using sleep extension intervention under a randomized controlled design.**

Our novel technology-assisted sleep intervention was developed to leverage a rapidly increasing public interest in sleep tracking, especially wearable sleep tracker use by consumers (+500% in 3 years). Our technology employs four elements -- a wearable sleep tracker, didactic content, an interactive smartphone application and brief telephone counseling . This study will randomize 60 non-diabetic women with a history GDM who report short sleep duration to an eight-week sleep extension intervention group or a healthy living information control group. We hypothesize that this sleep extension intervention will be feasible, acceptable and improve glucose metabolism.

### **3.0 Objectives/Aims**

The specific aims are to determine:

**Aim 1:** Feasibility and acceptability of sleep extension intervention. Rationale: Analysis of recruitment, retention and participant program evaluation will provide feasibility and acceptability data. Hypothesis: Sleep extension intervention will be feasible and acceptable to the target population. Approach: Feasibility will be determined through analysis of recruitment and retention. Acceptability will be determined through participant evaluation.

**Aim 2:** Efficacy of sleep extension intervention on primary outcomes of glucose metabolism. Rationale: Short sleep duration was associated with abnormal glucose metabolism in women with previous GDM. Sleep optimization in short sleeping individuals without diabetes resulted in improved insulin resistance. Hypothesis: Sleep extension intervention will result in improved glycemic control. Approach: A randomized controlled trial of an 8-week sleep extension intervention compared to a healthy living information control group on glucose metabolism as measured by an oral glucose tolerance test and A1C at baseline and at the end of intervention.

**Aim 3:** Efficacy of sleep extension intervention on secondary outcomes of weight, appetite regulating hormones, energy expenditure, inflammatory markers, depressive symptoms and subjective sleep quality.

### **4.0 Eligibility**

We will recruit 60 subjects for this study

#### **4.1 Inclusion Criteria**

- Premenopausal women, age 18-45, with a history of GDM who currently do not have diabetes
- At least one year post-partum
- Reported habitual sleep duration <7h/night during work- or weekdays with a desire to sleep longer
- Reported time spent in bed  $\leq$ 8 h
- Own a smartphone compatible with Fitbit.
- No need to provide care at night for her child(ren), defined as >3 times per week and > 30 minutes at a time
- No history of obstructive sleep apnea, insomnia, or restless leg syndrome
- No use of sleeping medications or sleep aids

#### **4.2 Exclusion Criteria**

- A1C  $\geq$ 6.5%
- Currently pregnant or planning pregnancy or breast feeding
- Insomnia symptoms defined as severe as assessed by the Insomnia Severity Index (score  $\geq$ 15)
- Rotating shift or night shift work
- High risk for obstructive sleep apnea screened by STOP BANG questionnaire.
- Significant medical morbidities, such as congestive heart failure, cirrhosis, chronic obstructive pulmonary disease requiring oxygen, active treatment for cancer or psychiatric problem, history of stroke with neurological deficits, cognitive impairment, kidney failure requiring dialysis, illicit drug use.

#### **Eligibility determination and source of subjects**

- Subjects will come from those receiving care at UIHealth and those responding to advertising materials (please see subject enrollment in the following section 5)
- Inclusion/exclusion criteria will be obtained by participant self-report on all criteria except A1C and urine pregnancy test which will be obtained by a blood and urine test. For those with medical records at UIC (please see subject enrollment in the following section 5), medical record review will be performed by study personnel.
- Study personnel will assess subjects for eligibility by study inclusion and exclusion criteria. Those ineligible will not be pursued. A password protected file will be maintained of subjects approached but not interested, and those who expressed interest but did not meet inclusion/exclusion criteria.

#### **4.3 Excluded or Vulnerable Populations**

- Non-English speaking subjects- unable to participate in questionnaires

#### **5.0 Subject Enrollment**

- *Describe screening and enrollment.*
- *Describe from where subjects will be recruited and any advertising or recruitment materials that will be used.*
- *Describe what happens with screen failures and any data obtained from screen failures.*
- *Describe the methods to minimize coercion and undue influence on the subjects.*
- *Describe the procedures to separate clinical responsibilities and influence from research responsibilities and influence.*

We will employ the following recruitment/enrollment methods:

1. Passive Advertising: We will distribute study advertisement materials throughout UI Health and local health centers, including clinical environments. Emails through UIC email system will be used. Individuals will call research assistants (RAs) or principal investigator (PI) or co-PIs for eligibility assessment by phone.
2. Active Recruitment in Clinical Sites within UIHealth: On-site RAs will receive additional referrals directly from staff or patients interested in the study. In these situations, PI, co-PIs or RAs will discuss the study and assess eligibility in a private exam room within the clinic before or after a clinical encounter. Additionally, we will work with Mile Square Health Centers to screen the appointment list of patients visiting the clinics. Potential eligible subjects will be identified by EMR and PI/RAs will discuss the study at the visit as described.
3. Active Recruitment from Registries: The research assistants will work from a CCTS-approved list of patients with previous GDM, identified from the electronic medical record. A list of UIC patients with a history of gestational diabetes or abnormal 3-hour oral glucose tolerant test in the past 10 years will be obtained from CCTS. In addition, CCTS will retrieve a list of patients with a diagnosis of gestational diabetes from July 2018 onwards throughout the duration of this protocol. This is essential to identify potential subjects and without this information, the research will be very difficult to conduct. The information from CCTS will include diagnoses, laboratory report (of glucose values and HbA1c), name, age, medical record numbers, address and phone numbers. Medical records will then be reviewed to ensure eligibility. We will send letters informing patients that they may be eligible for the study and may opt-out of further contact. After one week of mailing the letters, those who do not opt out will be contacted by the RAs to assess interest and eligibility. In addition, if the potentially eligible subjects have an appointment at UIC clinics, a research assistant will go and meet with the subjects either before or after the appointments and ask if they may be interested in hearing more about the study using the approved script. If the subjects express interest but do not have time, a flyer will be given to them if

they would like. If they would like to be contacted at a later time, an arrangement will be done with the RA.

4. Online Recruitment: will be done through <https://www.researchmatch.org/>. Potential subjects will contact investigators via email or telephone, after which eligibility will be determined as above.

### **Screening**

- Upon a contact with subjects believed to be eligible, PI, co-PI or RA will inquire about potential interest in study participation following the IRB approved recruitment script. They will be screened verbally for inclusion/exclusion criteria utilizing an IRB approved script (see Eligibility check list and Recruitment script). If the subject is eligible and interested, study personnel will review the study in detail, using an IRB approved consent form as guidance, plan for informed consent form (ICF) signing and study participation dates if appropriate.
- It will be made clear on initial contact that participation is entirely voluntary and that acceptance or decline will not impact the care they receive at UIHHSS.
- A password protected file will be maintained of subjects approached but not interested, and those who expressed interest but did not meet inclusion/exclusion criteria.

## **6.0 Study Design and Procedures**

### **Additional screening for eligibility**

- After informed consent is obtained, the participants will undergo additional screening including A1C and urine pregnancy test. These will be done with spot urine samples and finger stick or blood tests. If the A1C test from the finger stick is abnormal ( $\geq 6.5\%$ ), blood test (5 ml) will be done to confirm eligibility.

### **Study protocol**

#### **1. Baseline assessment:**

- One week of actigraphy will be recorded using an actiwatch spectrum. If during this assessment it is found that their sleep duration is  $\geq 7$  hours during the weekdays or work days, they will not be able to participate further.
- Subjects will answer sleep, physical activity, depression questionnaires, quality of life, anxiety symptoms and perceived stress symptoms.
- Weight, height, waist and hip circumference, and neck circumference will be obtained
- Eating behaviors, appetite and 24 hour food recall will be obtained through questionnaires.
- 
- At the end of one week, they will return to have a 75-gram oral glucose tolerance test (OGTT) done at the clinical research center (see below procedure).

- Blood will be assayed for A1C, serum creatinine, lipid panel and CBC.
- Blood will be saved for assay for genetic analysis, appetite regulating hormones (leptin, ghrelin, PYY, 2-arachidonoylglycerol (2-AG)), and inflammatory markers (CRP, IL-1, IL-6), and metabolomics profiles.
- Stool sample will be collected for stool microbiome assay
- Resting metabolic rate will be performed
- Additional serum samples will be stored for future analysis

2. The subjects will then be randomized to healthy living control group or sleep extension group for 6 weeks (see blow detail).
3. At week 6, they will be given an actiwatch to wear for one week. At week 7, the following procedures will take place
  - They will return to the CRC to have a repeated 75-gram OGTT done.
  - Weight will be obtained
  - Subjects will answer sleep, depression questionnaires, quality of life, anxiety symptoms and perceived stress symptoms.
  - Eating behaviors, appetite and 24 hour food recall will be obtained through questionnaires.
  - Blood will be assayed for A1C, lipid panel.
  - Blood will be saved for later assay for appetite regulating hormones (leptin, ghrelin, PYY, 2-arachidonoylglycerol (2-AG)), and inflammatory markers (CRP, IL-1, IL-6) and metabolomics profiles.
  - Stool sample will be collected for stool microbiome assay
  - Resting metabolic rate will be performed
  - Additional serum samples will be stored for future analysis
  - Participant evaluation of the program will be obtained through questionnaires and interview.
4. At week 10, subject will be given an actiwatch for one week. And,
  - They will return to the CRC to have fasting glucose and insulin level done.
  - Weight will be obtained
  - Subjects will answer sleep, depression questionnaires, quality of life, anxiety symptoms and perceived stress symptoms.
  - Blood will be saved for later assay for appetite regulating hormones (leptin, ghrelin, PYY, 2-arachidonoylglycerol (2-AG)), and inflammatory markers (CRP, IL-1, IL-6) and metabolomics profiles.

**Study procedures:** are detailed as follow

**1. Questionnaires:** Participants will complete standardized questionnaires. The Pittsburgh Sleep Quality Index (PSQI) assesses sleep quality in the past month, Epworth Sleepiness Scale (ESS) assesses daytime sleepiness, PROMIS Sleep questionnaire, Insomnia Severity Index (ISI) assesses insomnia symptoms, the STOP BANG questionnaire assesses risk of obstructive sleep apnea, the Center for Epidemiological Studies Depression (CESD) assess depressive symptoms, quality of life, anxiety symptoms (GAD-7), perceived stress scale, PROMIS fatigue scale.

Three factor eating questionnaires and Internal Physical Activity Questionnaires (IPAQ) will also be collected. ISI and STOP BANG will be used to screen for eligible participants. PROMIS, PSQI, ESS, Eating questionnaire, IPAQ and CESD will be given at baseline and at the end of the protocol.

**2. Wrist actigraphy to measure behavioral sleep** Participants will wear an Actiwatch Spectrum Plus (Respironics, USA) on their non-dominant wrist for one week during baseline assessment, and at week 6 and week 10. Data will be collected in 30-sec epochs. Subjects will be asked to keep a daily sleep log and press an event marker on the Actiwatch at bedtime and wake-up time. Data will be downloaded and reviewed with each participant to clarify inconsistencies when the Actiwatch is returned. Rest intervals will be set using reported try-to-fall-asleep times and wake-up times on daily sleep logs or event markers if these times are missing. Using the Immobile Minutes algorithm in the Actiware 6 software, we will derive the following outcome variables: sleep onset, sleep offset, sleep duration, sleep efficiency (a measure of sleep quality), mid-sleep time (time point between sleep onset and wake time), and standard deviation (SD) of sleep duration, an indicator of sleep regularity which we previously showed to be related to glucose metabolism.

**3. Oral Glucose Tolerance Test (OGTT).** After an overnight fast, the subject will arrive at the CRC between 8-9 am. Blood samples will be obtained at 0 minutes for glucose and insulin. Then 75 grams glucose solution will be given orally. Blood samples will be obtained at 30, 60, 90, 120 minutes for glucose and insulin. Extra blood samples will also be obtained at 0 minutes and stored for further analysis. **Total blood volume 60 ml per one OGTT visit.**

**4. Blood samples** will be obtained for lipid panel, creatinine and A1C at baseline and at week 6. CBC will be obtained at baseline. Fasting glucose and insulin will be obtained at week 10. Blood will be saved for later assay for genetic analysis, appetite regulating hormones (leptin, ghrelin, PYY, 2-arachidonoylglycerol (2-AG)), and inflammatory markers (CRP, IL-1, IL-6) and metabolomics profiles. **Total blood sample 20 ml at each visit.**

**5. Microbiome** Stool samples to measure the gut microbiome will be collected at week 0 and week 6. Changes in sleep may alter the gut microbiome and potentially influence glycemia. Participants will be provided a collection device (Easysampler®, ALPCO, Inc.) and return the specimen at a subsequent visit. Remaining stool samples will be stored in a freezer at the College of Medicine for later analysis by UIC researchers.

**6. Resting energy expenditure:** Oxygen consumption will be measured through indirect calorimetry using the Vyntus CPX system metabolic cart (Vyaire Medical, Mettawa, IL). In this test, a canopy hood is placed over the subject's head as he/she reclines in bed. One end of the canopy has tubing connected to the metabolic cart, while the other end of the canopy is open to room air. During the 30-40 minute procedure, expired gases are measured and resting energy expenditure is calculated using the Harris-Benedict equations. This will be performed during fasting.

**7. Feasibility and acceptability of Sleep extension:** Feasibility will be determined through analysis of recruitment (number recruited, screened, eligible, and consented) and retention (% session participation, program completion rates). Acceptability will be determined through participant evaluation (written evaluation and interview at program completion). See Appendix B.

**8. Intervention Description: Sleep Extension** The goal of sleep extension is to increase sleep time by  $\geq$  30 minutes. Participants randomized to the intervention will receive: (1) a wearable sleep tracker; (2) a smartphone application with interactive feedback and tools; (3) didactic content including weekly email lessons, reminders, and notifications; and (4) brief telephone coaching. The components are described below.

**8.1 Wearable sleep tracker:** A Fitbit Alta HR wearable sleep tracker allows participants to track their sleep and share results with the coach, not for the main study outcome (measured with actigraphy). Consumer sleep trackers provide an estimation of sleep but are less precise than actigraphy devices. Therefore, our main outcome will be measured with actigraphy, which is validated but does not provide real-time feedback to the wearer. Fitbit data will be used in coaching sessions and for providing weekly reports. The coach will have access to participants' sleep tracker data through a dashboard using the Fitabase platform.

**8.2 Smartphone application:** Participants will download the Fitbit smartphone application on their smartphone and participate in brief training in the intervention orientation session. Participants will be trained to review and edit their Fitbit sleep log each day, increasing the data validity. Though the application has the ability to enter sleep goals, these features will not be set on participants' applications.

**8.3 Intervention content:** Participants will receive automated content, including didactic lessons (weekly), individualized progress reports (weekly), and bedtime reminder text messages (30 min before scheduled bedtime; can be disabled for Weeks 4-6). The intervention content was developed by psychologists with advanced training in sleep and behavior change ([name] and [name]) and has been piloted in initial user testing. The 6 weekly didactic lessons (estimated duration 8-10 min), of written and video didactic content will be delivered via email and can be viewed on a smartphone, desktop, or tablet. Content from the lessons will be reinforced in the telephone coaching sessions (see Appendix A). Participants will receive an automatically generated report each week detailing their days of device usage, average bedtime, wake time, sleep duration, and an encouraging statement linked to weekly didactic content. They will be asked to fill the visual analog scale for hunger one day per week (once in the morning before breakfast and once before bedtime).

**8.4 Coaching:** All participants will be assigned to a sleep coach to monitor their progress during the study and provide weekly telephone coaching sessions related to their sleep-related goals. *Drs. [name] and [name] will act as coaches for this pilot.* The coaching protocol, developed by [name], is based on the principles of Supportive Accountability. The coach will establish **legitimacy** by their knowledge of

sleep and basic counseling principles. They will establish **goals** with the participants based on the participants' values and beliefs, including sleep-related goals and usage goals (e.g., number of days wearing the sleep tracker). **Performance monitoring** will be completed through an online dashboard visible to the coach (Fitabase Inc.). The dashboard will contain data from sleep diaries and the wearable sleep tracker. The first coaching session will be a 20-min engagement session, which includes introductions, rationale for the program, roles of the coach, and the participants' goals for the program. Coach will provide feedback to the participant based on wearable sleep tracker data. For coaching sessions 2-8, the coach and participant will also have weekly brief (5-10 min) follow-up support calls to review progress, problem solve barriers to progress, and set goals for the following week. Between sessions, coach will be available to troubleshoot any problems. The use of coaching has been demonstrated to improve adherence to technology-based interventions. Drs. [name] and [name] have extensive experience in the use of coaching to improve adherence to technology-based interventions.

8.5 Hunger rating based on visual analog scale (0-100) will be given to the subjects to fill one day per week, in the morning before breakfast and before bedtime.

**9. Attention control: Health Education.** Use of a control group is to control for the coach contact in the intervention group. Participants assigned to the control group will be provided weekly health education emails (e.g., nutrition, stretching exercises; Appendix A). They will be instructed to maintain their sleep schedule but not monitored with diaries or coaching, a technique that produces little change in sleep timing. Participants will receive weekly brief telephone contact from the coach ( $\leq 5$  min) to answer questions. They will be asked to fill the visual analog scale for hunger one day per week (once in the morning before breakfast and once before bedtime). After the final follow-up, control participants will receive a Fitbit fitness tracker and PDF files of the 6 didactic lessons by mail.

All procedures in the protocol are research related. The research will take place at the College of Nursing, [name] or at the Clinical Research Center.

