### **Protocol Overview**

	Urine preg test Screening questionnaire	A1C	OGTT, and blood samples	Questionnaires, actigraphy (1 week)	Stool sample	Energy expenditure	Acceptability assessment
Screening	X	X					
Week 0-1		X	X	X	x	x	
RANDOMIZATION							
Week 6-7		X	X	X	x	x	X
Week 10			Fasting glucose and insulin	X			

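### Resting energy expenditure is measured by calorimetry, but the only calculation stated for it, the Harris-Benedict equations, uses no gas measurement

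*Combined protocol and SAP*

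**What the plan says.** Aim 3 (Section 3.0) concerns efficacy on "secondary outcomes of weight, appetite regulating hormones, energy expenditure, inflammatory markers, depressive symptoms and subjective sleep quality". Energy expenditure and weight are therefore separate secondary outcomes. Section 2.0 gives the reason for interest: among the likely routes from insufficient sleep to diabetes risk it names "changes in energy expenditure and abnormal adipocyte function".

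The measurement is described in Section 6.0, Study procedures, item 6: "Oxygen consumption will be measured through indirect calorimetry using the Vyntus CPX system metabolic cart". The participant lies fasting under a canopy hood for 30-40 minutes. The item then gives the calculation: "expired gases are measured and resting energy expenditure is calculated using the Harris-Benedict equations".

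The other mentions only schedule the test. The visit list in Section 6.0 says "Resting metabolic rate will be performed" at baseline and again at week 7. The Protocol Overview table has a column headed "Energy expenditure", marked at Week 0-1 and Week 6-7. Section 12.0 deals with glucose parameters only and gives neither a derivation nor an analysis for this outcome.

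**The concern.** Item 6 joins a measurement to a formula that cannot use it. Indirect calorimetry obtains energy expenditure from gas exchange. The Harris-Benedict equations are prediction equations: they take sex, weight, height and age and return an expected value. That is a property of the named method; the protocol neither defines nor cites it.

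If the sentence were followed, two calorimetry sessions per participant would not enter the outcome they were scheduled for. The reported change would be a rescaled weight change, so Aim 3 would count weight twice. A real shift in metabolic rate at stable weight, which is the kind of effect the background section makes of interest, could not appear. A reader of the results also could not tell whether the measured or the predicted value had been prespecified.

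**Working it through.** The documents give no figure for this outcome, so there is nothing to reproduce. The check has two parts: a comparison of the texts, then the algebra of the literal reading.

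**1. Texts side by side**

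| Place | What it gives | Derivation? |
|---|---|---|
| Section 3.0, Aim 3 | Energy expenditure as a secondary outcome, beside weight | No |
| Section 6.0, visit list | Test at baseline and week 7 | No |
| Section 6.0, item 6 | Oxygen consumption and expired gases measured | Harris-Benedict |
| Protocol Overview | Test at Week 0-1 and Week 6-7 | No |
| Section 12.0 | Glucose parameters only | No |

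Item 6 is the only place that states a rule.

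**2. Inputs available at each visit.** At baseline, "Weight, height, waist and hip circumference, and neck circumference will be obtained". At week 7 the list has only "Weight will be obtained". Height is taken once, so it cancels from any change score.

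**3. Form of the literal outcome.** For women the equation has the form

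predicted value = a + b × weight + c × height − d × age,

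so the change from baseline is

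change = b × (weight change) − d × (age change).

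Assumptions not in the documents: b = 9-10 kcal/day per kg and d = 4-5 kcal/day per year.

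**4. Weight term**

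| Weight change (illustrative) | b = 9 | b = 10 |
|---|---|---|
| 1 kg | 9 kcal/day | 10 kcal/day |
| 2 kg | 18 kcal/day | 20 kcal/day |
| 5 kg | 45 kcal/day | 50 kcal/day |

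The documents give no expected weight change; these values only show the scale.

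**5. Age term, stable weight.** With exact age over 6 to 7 weeks, the fall is 4 × 6/52 = 0.46 to 5 × 7/52 = 0.67 kcal/day. With age in completed years it is zero unless a birthday falls between the visits. That applies to 6/52 = 11.5% to 7/52 = 13.5% of women, or 6.9 to 8.1 of 60 if all complete both tests, each shifted by 4-5 kcal/day.

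**6. Spot check inside the assumed ranges.** Two coefficient pairs were evaluated for a woman of 163 cm and 35 years over 7 weeks: b = 9.247 with d = 4.330, and b = 9.5634 with d = 4.6756. They give −0.6 kcal/day at stable weight, +8.7 to +8.9 for a gain of 1 kg, and −9.8 to −10.2 for a loss of 1 kg. The results are the same at baseline weights of 65, 80 and 95 kg, as the linear form requires.

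**7. What this means for a comparison of the arms.** With exact age and a common interval, the age term is the same constant for everyone and cancels between arms. The outcome is then b times weight change plus a constant. A t-test on change would return the same t statistic and p-value as a t-test on weight change. Completed-year age or unequal visit intervals add a little noise, so the link is close but not exact.

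**The case against.** The strongest reply is that this is a slip of the pen. Everything around the sentence points to measured expenditure: the metabolic cart, the hood, the fasting test, the collection of expired gases and the repeat at week 6-7. None of that is needed to predict a value from weight, height and age, and weight is already taken at both visits. On that reading the sentence describes one procedure in two steps with the wrong equation name, and nobody at the site would discard the gas data. The size calculations then illustrate a reading that is probably not intended, with coefficients the protocol does not supply, and the age and birthday figures affect no decision.

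Much of this stands. Misnaming is the likelier explanation, the coefficients are assumptions, and the age term matters only in showing that the tie to weight is not perfect. What does not follow is that the text can stay. The documents do not say which equation was meant, or whether Harris-Benedict was intended as a reference value alongside the measurement. An analyst who follows the written rule would use the predicted value, and no other text would correct that choice. The structural point also holds without exact coefficients: any formula in weight, height, age and sex leaves weight as the only input in the protocol's schedule that can move appreciably between the visits.

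**Conclusion.** The concern holds. The calculation stated for resting energy expenditure does not use the calorimetry described in the same item, and it is the only derivation given for a prespecified secondary outcome.

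If the equation is merely misnamed, this is a wording error with no effect on the data; the documents give no basis for putting a probability on that. If it is followed literally, the change score carries almost no information beyond weight change. The first conclusion rests only on what the named equations take as inputs. The kcal/day figures rest on the assumed coefficient ranges.

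The damage is confined to one secondary outcome and can be undone later if the gas data are kept. The primary glucose outcomes, the sample size and the power are unaffected.

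**What to change.** First confirm which expired gases the cart records, since item 6 names only oxygen consumption and otherwise leaves the gases unspecified. Then replace the sentence in Section 6.0, item 6, with one stating that resting energy expenditure at baseline and at week 6-7 is calculated from the measured gas exchange with a named calorimetry equation (for example Weir), and which gas measurements enter it. If the Harris-Benedict value is wanted, describe it as a predicted reference value and not as the outcome.

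The cost is that check and one sentence. The test is already scheduled at both time points, so no visit or procedure is added. Until the text is settled, the gas data should be kept so that the outcome can be derived from them.
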